### **3. DESCRIPTION OF DESIGN AND TRIAL POPULATION**

#### **3.1 OVERALL TRIAL DESIGN AND PLAN - DESCRIPTION**

Due to the methodology of this trial (dose escalation), it is not possible to predict the number of patients necessary to reach the objectives. An estimated total of up to 80 patients might be necessary to establish MTD. A total of 24 patients will be treated at MTD. Actual accrual will depend on the number of dose levels tested and the adverse events observed. Patients non evaluable with respect to MTD will be replaced. Patients with a histologically or cytologically confirmed diagnosis of a malignant solid tumour refractory or not amenable to standard therapies are eligible for this trial. It is planned to have the trial performed at one centre, depending on enrolment more centres may be initiated.

#### **3.2 DISCUSSION OF TRIAL DESIGN, INCLUDING THE CHOICE OF CONTROL GROUP(S)**

This is an open label, uncontrolled trial in patients with advanced solid tumours following a fixed dose escalation design. The aim of this trial is to assess the MTD of BI 6727 administered at escalating doses using a toxicity-guided approach.

#### **3.3 SELECTION OF TRIAL POPULATION**

Patients with advanced solid tumours will be eligible for this trial.

A log of all patients screened will be maintained in the ISF at the investigational site.

##### **3.3.1 Inclusion criteria**

- 1) Patients with confirmed diagnosis of advanced, non resectable and / or metastatic solid tumours, who have failed conventional treatment, or for whom no therapy of proven efficacy exists, or who are not amenable to established forms of treatment
- 2) Age 18 years or older
- 3) Written informed consent consistent with ICH-GCP and local legislation
- 4) Eastern Cooperative Oncology Group (ECOG, R01-0787) performance score  $\leq 2$
- 5) Recovery from CTCAE Grade 2 - 4 therapy-related toxicities from previous chemo-, hormone-, immuno-, or radiotherapies (except alopecia)

The 18 additional patients recruited at the MTD must also meet the following criterion:

- 6) Measurable tumour deposits (RECIST) by one or more techniques (CT, MRI)

##### **3.3.2 Exclusion criteria**

- 1) Serious illness or concomitant non-oncological disease considered by the investigator to be incompatible with the protocol
- 2) Pregnancy or breastfeeding
- 3) Active infectious disease or known chronic Hepatitis B/Hepatitis C infection
- 4) Clinical evidence of active brain or leptomeningeal disease during the past 12 months

- 5) Second malignancy currently requiring active therapy
- 6) Absolute neutrophil count less than 1500 / mm^3
- 7) Platelet count less than 100 000 / mm^3
- 8) Bilirubin greater than 1.5 mg / dl (> 26 µmol / L, SI unit equivalent)
- 9) Aspartate amino transferase (AST) and / or alanine amino transferase (ALT) greater than 2.5 times the upper limit of normal (if related to liver metastases greater than five times the upper limit of normal)
- 10) Serum creatinine greater than 1.5 mg / dl (> 132 µmol / L, SI unit equivalent)
- 11) Known history of relevant QT-prolongation, e.g. long QT-syndrome
- 12) Women and men who are sexually active and unwilling to use a medically acceptable method of contraception
- 13) Treatment with other investigational drugs or participation in another clinical trial within the past four weeks before start of therapy or concomitantly with this trial (except for present trial drug)
- 14) Chemo-, radio or immunotherapy within the past four weeks before start of therapy or concomitantly with this trial. This restriction does not apply to steroids and bisphosphonates.
- 15) Patients unable to comply with the protocol
- 16) Active alcohol or drug abuse

### 3.3.3 Retreatment criteria

Patients with a clinical benefit after a course of BI 6727 (clinical response, absence of progression or symptom improvement) and who have recovered from any clinically relevant drug-related AE are eligible for a further treatment course. In case of symptom improvement despite disease progression a repeated course may be allowed in agreement between the clinical monitor and the investigator.

Patients experiencing DLT are eligible for further treatment courses with BI 6727 at one dose tier below as soon as recovery from drug related toxicities allows further treatment. Patients eligible for a further (repeat) treatment course will not start treatment before 22 ( $\pm$  2) days after start of the previous course. If an interruption of more than 6 weeks as counted from the start of the previous treatment course is necessary, the patient must be removed from this trial.

## 4. TREATMENTS

### 4.1 TREATMENTS TO BE ADMINISTERED

#### 4.1.1 Identity of investigational product(s)

Substance (INN): BI 6727  
Pharmaceutical form: Solution for infusion  
Source: Boehringer Ingelheim Pharma GmbH & Co. KG  
Unit strength: 0,5 mg /mL (vials with 100 mL).  
Daily dose: See section 4.1.3  
Duration of use: Single dose  
Route of administration: intravenous  
Posology: Infusion over 60 min

#### 4.1.2 Methods of assigning patients to treatment groups

Not applicable. This is a dose escalation trial.

#### 4.1.3 Selection of doses in trial

##### 4.1.3.1. First course of administration of BI 6727

The starting dose will be 12 mg. As long as no patient of an ongoing dose tier develops drug-related toxicity beyond Grade 1 according Common Terminology Criteria for adverse events (CTCAE) during the initial treatment course the dose will be escalated by up to 100% in new patients. As soon as any patient of an ongoing dose tier experienced drug-related toxicity Grade 2 or higher escalation steps of not more than 50% will be allowed thereafter. Should dose limiting toxicity (DLT) be observed in 1/6 patients treated in a cohort and escalation continues this will be in steps of not more than 35%. Before entering patients at a higher dose level it will be ensured that all patients at an ongoing dose level have completed the initial course of BI 6727 dosing. The decision regarding the incremental size of the dose escalation steps will only be taken after discussion between the sponsor and the clinical investigator considering toxicity data from each patient cohort. Prior to inclusion of a new patient the investigator has to confirm the respective dose with the clinical monitor of the sponsor.

##### 4.1.3.2. Additional courses of BI 6727

The dose of BI 6727 will be the dose administered in the previous course, unless the patient experienced dose limiting toxicity. Patients experiencing DLT are eligible for further treatment courses at one dose tier below.

#### 4.1.4 Selection and timing of doses for each patient

Each vial of BI 6727 contains 100 mL of a 0.5 mg/mL solution.

The procedure to prepare the infusion solution is the following:

Determine the amount of solution which needs to be added to the 500 mL infusion bags according to the dose level (e.g. dose of 12 mg = 24 mL Volume).

Withdraw the respective amount of NaCl 0.9% from the infusion bag.

Add the respective amount of BI 6727 solution to the infusion bag and mix

Take a 5 mL sample (corresponding to 1% total volume) out of the mixed prepared ready to use solution and store (the sample should not be cooled or frozen). The sample needs to be labelled with the right pre-printed, adhesive label.

Solution is ready to be infused to the patient by using an infusion pump (infusion duration 60 minutes).

#### **4.1.5 Preparation of the infusion solution and of the sample for analysis.**

Each vial of BI 6727 contains 100 mL of a 0.5 mg/mL solution.

The procedure to prepare the infusion solution is the following:

Determine the amount of solution which needs to be added to the 500 mL infusion bags according to the dose level (e.g. dose of 12 mg = 24 mL Volume).

Withdraw the respective amount of NaCl 0.9% from the infusion bag.

Add the respective amount of BI 6727 solution to the infusion bag and mix

Take a 5 mL sample (corresponding to 1% total volume) out of the mixed prepared ready to use solution and store (the sample should not be cooled or frozen). The sample needs to be labelled with the right pre-printed, adhesive label.

Solution is ready to be infused to the patient by using an infusion pump (infusion duration 60 minutes).

#### **4.1.6 Selection and timing of doses for each subject**

BI 6727 will be administered as a short infusion over 60 minutes using an infusion pump, on day 1 of each course (the start and end time of the infusion needs to be documented in the e-CRF). Immediately following the infusion of BI 6727 the infusion tubing will be washed with 100 mL physiological sodium chloride (0.9% NaCl) solution for a maximum duration of 10 minutes (The end time of the washing step needs to be documented in the e-CRF). BI 6727 should be administered strictly intravenously.

Initially, three patients will be treated per dose level. When at the ongoing dose level one patient experiences drug-related dose limiting toxicity (DLT; for definition, please refer to section 5.2.1) the number of patients treated at that dose level will be increased to a maximum of six evaluable patients. When no further patient experiences DLT the dose will be escalated to the next level. When two or more patients experience DLT in any dose cohort, other than the

expansion cohort at MTD level, enrolment into this dose cohort will be stopped. In order to define the maximum tolerated dose (MTD) three additional patients will be treated at one dose tier below unless six have already been treated at that dose tier. The MTD (see also section 5.2.1) is the highest dose at which not more than one patient out of six experiences DLT (R01-0028). Should safety data of patients treated at the next lower dose indicate a sufficient safety margin another escalation to an intermediate dose can be chosen after discussion between the investigator and the clinical monitor.

Once the MTD is determined patient enrolment at higher dose tiers will be suspended. Further patients will be included at the MTD level until a total of 24 patients will have been treated at the MTD.

#### **4.1.7 Blinding**

Not applicable, this is an open label trial.

#### **4.1.8 Packaging, labelling and re-supply**

BI 6727 will be supplied in 100 mL vials containing 50 mg BI 6727, respectively. Medication will be labelled with: trial number, medication number, contents, name and strength of product, pharmaceutical dosage form, route of administration, directions for use, storage conditions, term "for clinical trial use only", use-by date, batch number and sponsor.

Examples of the labelling of the medication will be found in the investigator site file (ISF).

Medication will be delivered to the hospital's pharmacy where the total dose per patients will be prepared upon request from the investigator. The content of several vials may be needed for administration of the requested dose. For this purpose the medication will be filled in plastic bags prefilled with sodium chloride so that the trial drug can be administered as one single infusion to the patient. For details concerning the preparation of the infusion solution, please refer to section 4.1.4.

#### **4.1.9 Storage conditions**

BI 6727 will be stored in the hospital pharmacy in a limited access area at room temperature.

### **4.2 CONCOMITANT THERAPY**

Concomitant medications, or therapy to provide adequate care, may be given as clinically necessary.

All concomitant (non-oncological) therapies starting or changing during the course of the study are allowed but should be recorded in the e-Case Report Form (eCRF) except for vitamins, appetisers or nutrient supplements. Trade name, indication, and dates of administration will be documented. If patients receive parenteral nutrition during the study, the components need not be specified in detail. It should just be indicated as 'parenteral nutrition' and the form be completed. If a patient needs anaesthesia, it will be sufficient to indicate 'anaesthesia' without specifying the details.

#### **4.2.1     Rescue medication and additional treatment(s)**

Rescue medication to reverse the action of BI 6727 is not available. Potential side effects of BI 6727 have to be treated symptomatically (see also section 5.2). Symptomatic treatments of side effects or tumour-associated symptoms are allowed.

#### **4.2.2     Restrictions**

Additional chemo-, immuno-, hormone - or radiotherapy is not allowed during the study. These restrictions do not apply for steroids and bisphosphonates. For symptom control palliative radiotherapy may be permitted after discussion with the BI Clinical Monitor.

For patients of the expansion cohort at MTD, the impact of any palliative radiotherapy administered on evaluable lesions has to be documented.

### **4.3       TREATMENT COMPLIANCE**

The study medication will be administered as a single intravenous 60 minute infusion under supervision of the investigator or dedicated personnel.

## 5. OBSERVATIONS

Safety, pharmacokinetic and efficacy data will be collected and evaluated.

### 5.1 EFFICACY / CLINICAL PHARMACOLOGY

Efficacy as secondary endpoint will be assessed by analysing the tumour response to therapy and time to progression in all patients with measurable disease.

#### 5.1.1 PRIMARY ENDPOINT

Not applicable since this study focuses on safety endpoints. The primary endpoint for safety is described in section 5.2.1.

#### 5.1.2 SECONDARY ENDPOINTS

Response will be assessed by tumour measurements and will be evaluated according to the response evaluation criteria in solid tumours (RECIST, see ISF, R01-0754).

The investigator along with his / her radiologist will record the target and non-target lesions at baseline. One to ten target lesions should be identified at baseline and recorded in the eCRF. The same method of assessment and the same technique should be used to characterise each reported lesion at baseline and during follow-up. Lesions in previously irradiated areas may not be considered measurable at baseline. However, new lesions occurring in previously irradiated areas have to be considered for assessment of tumour response.

Response (complete response CR, partial response PR), stable disease (SD) and progression (progressive disease, PD) will be evaluated in this study using the international criteria proposed by the RECIST Committee. Changes in only the largest diameter (unidimensional measurement) of the tumour lesions are used in the RECIST criteria. For more details see also Appendix 10.4 "Tumour assessment according to RECIST".

## 5.2 SAFETY

### 5.2.1. Maximum tolerated dose (MTD) and dose limiting toxicity (DLT)

The maximum tolerated dose is defined as:

The dose of BI 6727 which is one dose tier below that dose at which two or more out of a maximum of six patients experienced DLT. At the maximum tolerated dose, no more than one patient out of six patients may experience DLT, i.e. MTD is defined as the highest dose studied for which the incidence of dose-limiting toxicity is no more than 17% (i.e. 1/6 patients) during the first course.

For definition of DLT, it is essential that patients are treated sufficiently according to supportive care standards. Patients with treatable adverse events that are not sufficiently treated need to be replaced.

Dose limiting toxicity is defined as:

- drug related CTCAE grade 3 or 4 non haematological toxicity (except emesis or diarrhoea responding to supportive treatment), or
- drug related CTCAE grade 4 neutropenia for seven or more days and / or complicated by infection, or
- CTCAE Grade 4 thrombocytopenia .

The MTD will be defined on the basis of DLT observed during the first course of dose escalation cohorts. However, for those patients who receive a further infusion, unusual or unexpected toxicities will be considered for the purposes of confirming the MTD.

Patients with a clinical benefit after a course of BI 6727 (symptom improvement, clinical response or absence of progression) and who recovered from drug related adverse events are eligible for a further treatment course. In case of symptom improvement despite disease progression a repeated course may be allowed in agreement between the clinical monitor and the investigator. All DLT's occurring during the first or repeated treatment courses will be reported as significant adverse events.

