An AE flag will be defined for patients who developed an AE that was CTCAE grade ≥ 3 , DLT, or serious AE (SAE).

An AE attribute "CTCAE grade 3/4 or 5 combined with drug relation" will be derived to avoid incorrect condensing. Consider, for instance, a patient with coincident drug-related abdominal pain with CTCAE 1, and non-related vomiting with CTCAE 3. Without the new attribute these AEs would be reported as drug-related Grade 3/4 under the SOC Gastrointestinal disorder. With the new AE attribute these AE would be excluded.

An additional AE attribute "Drug relationship combined with seriousness of the AE" is needed similarly to the AE attribute "CTCAE grade 3/4 or 5 combined with drug relation" described above.

Frequency of patients with AEs will be summarised by treatment, primary SOC and PT. Separate tables will be provided for patients with other significant AEs, for patients with significant non-serious AEs and for patients with SAEs. Additionally, there will be a summary table presenting maximum CTCAE grade for each AE, as well as patients who developed AEs with CTCAE grade greater than 3, DLT, SAE, and significant AEs.

AE of special interest (User-defined AE categories): these will be the same as for project 1216.P1 (BI 2536). Frequency tables and listings for these AE categories will be provided.

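### The non-haematological DLT criterion stops at grade 4, so a first-course drug-related death with no earlier qualifying event is not literally a DLT and is not clearly protected from replacement

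*Protocol*

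**What the plan says.** **DLT definition.** Protocol 5.2.1 gives a closed list of three criteria. The first is "drug related CTCAE grade 3 or 4 non haematological toxicity (except emesis or diarrhoea responding to supportive treatment), or" the second is drug-related grade 4 neutropenia that lasts at least seven days or is complicated by infection, and the third is grade 4 thrombocytopenia. Protocol 7.3.1 refers back to this list, and the visible SAP text gives no DLT definition of its own.

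**Grade wording elsewhere.** Protocol 4.1.3.1 is open-ended: after "drug-related toxicity Grade 2 or higher escalation steps of not more than 50% will be allowed thereafter". SAP 5.2.4 lists events of grade 3 and above. SAP 7.7.1.2 names grade 5 separately, in the attribute "CTCAE grade 3/4 or 5 combined with drug relation".

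**Replacement.** Protocol 3.1 says "Patients non evaluable with respect to MTD will be replaced". Protocol 6.3.1 replaces patients who are withdrawn or miss more than one first-course visit, leaves a single missed visit to discussion, and exempts only withdrawal because of DLT. It does not mention death. Protocol 7.3.1 says that patients evaluable for toxicity but not for efficacy do not have to be replaced. Protocol 5.2.1 separately requires replacement of patients whose treatable adverse events were not treated adequately.

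**Use of the count.** Under 4.1.6, one DLT among three patients expands the cohort to six: "When no further patient experiences DLT the dose will be escalated to the next level". Two or more DLTs stop enrolment into the cohort. Under 4.1.3.1, should DLT "be observed in 1/6 patients treated in a cohort and escalation continues this will be in steps of not more than 35" per cent, and no higher dose opens until "all patients at an ongoing dose level have completed the initial course of BI 6727 dosing". SAP 5.1 names DLT as the primary endpoint and bases the MTD on first-course incidence.

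**The concern.** A fatal toxicity is the most severe form of what the first criterion is meant to catch, yet as worded it falls outside. The wording used for step sizes and in the SAP shows that the documents can express an inclusive range, or name grade 5, where they want to.

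Replacement adds to the gap. If the death is not a DLT, the single exemption in 6.3.1 does not apply, and the patient could leave the denominator as well as the numerator. A dose with one counted DLT and one such death could then show 1/6, which is within the protocol's MTD limit. If that dose became the MTD, 4.1.6 says: "Further patients will be included at the MTD level until a total of 24 patients will have been treated at the MTD". With six already treated, that means 24 − 6 = 18 more patients, as 3.3.1 also states.

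**Working it through.** **1. The plan's own figure.** Table 7.6: 1 gives the chance of at least two DLTs in six patients, P = 1 − (1−p)^6 − 6p(1−p)^5. At p = 0.40, 0.42 and 0.45 this is 0.767, 0.797 and 0.836, against the stated 0.77, 0.80 and 0.84. It reproduces.

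**2. Which deaths fall outside the list.** Three kinds are already DLTs: a death after a recorded drug-related grade 3/4 non-haematological event (other than emesis or diarrhoea that responded to treatment), a death with qualifying grade 4 neutropenia, and a death with grade 4 thrombocytopenia. What remains is a first-course drug-related grade 5 event with none of these on record. The 5.2.1 provision for taking later unexpected toxicity into account covers only patients who receive a further infusion, so it does not reach this case.

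**3. What happens to that patient.** If visits after death are counted as missed, a death before visit 7 (day 15) misses visits 7 and 8, which is more than one, so 6.3.1 points to replacement. A death after visit 7 misses only visit 8, and replacement is then discretionary on the missed-visit rule. Against this, 3.1 aims replacement at patients not evaluable for the MTD, and 7.3.1 allows a patient evaluable for toxicity to be kept. The text therefore neither requires nor rules out keeping the patient.

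**4. Counts under the rules.**
- One other DLT plus one such death. Death counted: 2 DLTs, and enrolment into the cohort stops. Patient replaced: 1/6 once a seventh treated patient finishes course 1 without DLT, and escalation may continue by at most 35%.
- A lone such death in the first three. Death counted: 1/3, expansion to six, then at most 35% if no further DLT occurs. Patient replaced: 0/3 once a fourth treated patient finishes course 1 without DLT, then a step of at most 50%.

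**5. Chance of escalating, given exactly one such death in the first three.** Assume the other patients are independent, each with DLT rate r. The documents give no value for r, so a range is shown.
- Death counted: the two others and the three added patients must all be free of DLT, giving (1−r)^5.
- Patient replaced: the usual 3+3 rule applies to the evaluable patients, giving (1−r)^3 + 3r(1−r)^5.

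| r | death counted | patient replaced |
|---|---|---|
| 0.10 | 0.590 | 0.906 |
| 1/6 | 0.402 | 0.780 |
| 0.25 | 0.237 | 0.600 |
| 0.33 | 0.135 | 0.434 |
| 0.42 | 0.066 | 0.278 |

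At r = 1/6: (5/6)^5 = 0.402, and (5/6)^3 + 3(1/6)(5/6)^5 = 0.579 + 0.201 = 0.780. The replaced column takes the replaced patient as no longer bound by the course-completion condition in 4.1.3.1, and both columns ignore the sponsor-investigator discussion.

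**6. Average effect.** Let f be the share of DLT-level events that are deaths of this kind (assumed), with these patients replaced. The counted rate becomes q = p(1−f)/(1−pf). At p = 0.42 and f = 0.05, 0.10 and 0.20, P(at least 2 of 6) is 0.778, 0.758 and 0.712, against 0.797. Even f = 0.05 means 0.05 × 0.42 = 2.1% of all patients at that dose.

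**The case against.** The strongest reply is that nobody would read a drug-related death in a first-in-man trial as not dose limiting. Grade 3 or above is probably what the authors meant. Steps are agreed between sponsor and investigator after review of cohort toxicity (4.1.3.1), serious events are reported at once (8.4.1), and SAP 5.1 brings all information into the Phase II dose. The limiting toxicity of the related compound was neutropenia (1.2, 1.4), so the main expected fatal route is largely covered by the second criterion. All of this stands and limits the point to a rare case. None of it changes the definition or the denominator rule.

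A reader might infer that 6.3.1 makes replacement mandatory. The documents do not support that. The missed-visits section (6.2.4) describes a patient who later reports to the investigator, and a patient with fatal drug toxicity is naturally evaluable for toxicity under 3.1 and 7.3.1. Replacement is one reading.

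A reader might also infer that the patient could stay in the cohort as a non-DLT, giving 0/3 and an escalation chance of (1−r)^2 + 2r(1−r)^4, which is 0.86 at r = 1/6 and 0.43 at r = 0.42. That holds only if completing the initial course in 4.1.3.1 means receiving the infusion. SAP 5.3.3 would not count a course cut short by a non-DLT death before day 21 as completed, so these figures do not support the conclusion.

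Finally, the SAP refers to three amendments that were not supplied, and much of SAP 7.7.1.1 is redacted. The SAP's MTD limit (33%) already differs from the protocol's (17%), so the DLT text may also have been revised.

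**Conclusion.** The point holds as a minor, low-frequency safety correction. The literal definition leaves one kind of fatal first-course toxicity out of the primary endpoint, and the replacement rule does not clearly keep that patient in the denominator. The consequence is a possible record of 1/6 where there should be 2 DLTs. If the patient is replaced, the rule-only chance of escalating after one such death in the first three is 0.78 where it should be 0.40 (r = 1/6), or 0.28 where it should be 0.07 (r = 0.42).

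These contrasts are conditional on a rare event, on an assumed r, on replacement being chosen, and on no one intervening. The unconditional effect is small: 0.80 falls to 0.78 at an assumed 5% share. A reader might go further and conclude that the trial would escalate past a drug-related death, or that its MTD is unsound. The documents do not show that such a death occurred, and joint review makes such an escalation unlikely. Whether the gap was later closed cannot be determined from the supplied text.

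**What to change.** - Protocol 5.2.1: make the first criterion *drug-related CTCAE grade 3 or higher*, keep the emesis and diarrhoea exception, and add *or any drug-related death*.
- Protocol 6.3.1: state that any patient with a first-course DLT, including a fatal one, stays in the DLT denominator and is not replaced.
- Protocol 5.2.1: state that the requirement to replace inadequately treated patients does not apply to drug-related deaths. Without this, the two sections would conflict for an under-treated fatal event.
- SAP 7.7.1.1: use the same definition in the first-course DLT summary. If an amendment already does this, cite it. Because the SAP describes the trial conduct in the past tense, this line is the one that still bears on the reported result.

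The cost is about a line in each place, with no new data collection. The DLT count can only stay the same or rise. The downside is that a lone such death would expand the cohort, so up to three more patients would be treated at that dose.
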